2.2. Specific aims and hypotheses

The aim of this study is to test the hypothesis that obese pregnant women with weight gain above the IOM guidelines, 'High Gainers', will have increased energy intake but no evidence for changes in energy expenditure after adjustment for the weight gained when compared to women with appropriate gestational weight gain, 'Normal Gainers' (Figure 1).

Aim 1: Measure energy intake in obese women during pregnancy. The primary outcome is energy intake over the last 2 trimesters of pregnancy measured by: 1) the energy balance method (using doubly labeled water and change in maternal energy stores by whole-body MRI and fetus size by 3-D ultrasound) and, 2) our energy balance model of gestational weight gain and energy intake.

Hypothesis 1: Energy intake will be significantly larger in 'High Gainers' versus 'Normal Gainers'.

Aim 2: Measure total energy expenditure in obese women during pregnancy. We will combine the most accurate and precise methods to assess sedentary (sleeping metabolic rate in a room calorimeter) and free-living (doubly labeled water) energy expenditure, and physical activity.

[figure not shown]
Hypothesis 2: Absolute energy expenditure (unadjusted) during pregnancy will increase proportionally to increase in metabolic mass (mother plus fetus) whereas energy expenditure adjusted for maternal body energy stores and fetus size will not differ between 'High Gainers' and 'Normal Gainers'.

Aim 3: Measure energy intake and energy expenditure in obese women 12 months postpartum and their relationships to "postpartum weight loss".

Hypothesis 3: The percentage of weight normalization (postpartum weight loss as a percentage of gestational weight gain) will be proportional to the decreased energy intake from late pregnancy to 12 months postpartum.

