3. RESEARCH DESIGN

This is a single arm, prospective study. In this study, we will enroll up to 75 obese, pregnant women to complete at least 60. This study will be performed at Pennington Biomedical Research Center in Baton Rouge, Louisiana. Study outcomes will be assessed at three time points during pregnancy; namely, gestational weeks 13-16 (early), 24-27 (mid), and 35-37 (late); and at two time points postpartum; namely, postpartum weeks 22-25 and 48-56 (postpartum testing). Infants born to the mothers enrolled in the MomEE study will complete 1 study visit before 10 days of life to measure anthropometrics, body composition measurements, and questionnaires.

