8.8.3. MRI

Magnetic resonance imaging (MRI) will be performed using a 3.0 T scanner (General Electric, Discovery MR750w, Milwaukee, WI). Subjects will be placed supine on the scanner table with the arms above the head and legs propped up. Subject positioning will be taught and reviewed by a Maternal Fetal Medicine physician to ensure mother and fetal safety. A SPGRE weighted localizer and T1 8 point ME-FSPGRE images will be acquired through the anatomy from the tips of the fingers through the pubic symphysis (waist). The subject will then be repositioned on the table with the head propped up and the pubic symphysis (waist) and legs positioned flat on the table. A SPGRE weighted localizer and T1 8 point ME-FSPGRE images will be acquired from the pubic symphysis (waist) to the bottom of the feet. A total of approximately ~800-1100 T1 8 point ME-FSPGRE images will be acquired on each subject. A frequency of 256, phase of 256, and a field of view of 50 cm will be utilized for the scan. The slice thickness will be 10mm with 10mm interslice gaps. Scan time will be approximately 20-30 minutes with the total mean acquisition time, including positioning of the subject, approximately 30 minutes. Scans will be saved onto CD or DVD and sent to imaging department for analysis, but can also be sent to a third party for analysis. Scans will be performed per Pennington Biomedical SOP 1109. Any abnormal findings identified during scan acquisition or analysis will be documented and reported per this SOP and the incidental findings plan agreed upon by the collaboration of the Principal Investigator, [name], Co-Investigator, [name], and the Pennington Biomedical Imaging Director. These data will also have an additional layer of oversight as [name]. [name] will review each scan within 14 days of acquisition. [name]. [name] is a Co-Investigator of this study and the Director of the Maternal Fetal Medicine Department at Woman's Hospital and as such will follow his standard procedure for identification of an abnormal finding including fetal anomaly which is his area of expertise. This includes, but is not limited to, contacting the participant to discuss the finding, contacting the participant's physician and/or contacting the participant's obstetrician.

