10. DATA MANAGEMENT

10.1. Statistical power and sample size

The primary outcome is energy intake during pregnancy. We were able to apply the energy-balance model to

Table 4. Minimum sample size for power at .80 and .90, ratio between groups 1:2

Standard Deviation kcal/d	Mean Difference kcal/d	Power (β)	Group 1 N	Group 2 N
700	541	.90	27	54
700	468	.80	27	54
700	600	.90	22	44
700	520	.80	22	44
700	688	.90	17	34
700	590	.80	17	34

estimate energy intake in previously reported data on energy requirements during pregnancy [82]. The standard deviation of energy intake in the third trimester was conservatively estimated to be 700 kcal/d using Butte’s data on total energy expenditure and energy deposition of fat mass and fat-free mass.

We hypothesize that women who will exceed 2009 IOM recommendations for weight gain during pregnancy, the ‘High Gainers’, will have a larger energy intake than those who will keep their weight gain within IOM guidelines, the ‘Normal Gainers’. Because of the intervention, we predict to have a decrease in the incidence of ‘High Gainers’ from 66% to a rate below 50%. Therefore we predict that the ratio “High Gainers” to “Normal Gainers” will likely be 1:2. Our power/sample size analysis (Table 2) assumed: 1) power ≥ 0.90 , 2) alpha = 0.05, 3) the null hypothesis will be tested against a two-directional alternative, 4) the common standard deviation for energy intake is 700 kcal/d and 5) conservative estimates that the ratio between the two groups, ‘High Gainers’ to ‘Normal Gainers’ is 1:2.

As shown in Table 2, with subject assignment to the 2009 IOM guidelines being 1:2, we require a minimum of 51 subjects, to detect a between group difference of 590 kcal/d with 90% power or 520 kcal/d with 80% power. To allow for early deliveries, the inability to perform MRI in some subjects late pregnancy, due to limitations with the field of view, and that 10% of subjects will gain less weight than recommended; we aim to complete at least 60 subjects.

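### Energy-balance intake and adjusted expenditure need a late-pregnancy MRI that the plan expects to be unobtainable in some women, and no analysis rule covers them

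*Combined protocol and SAP*

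**What the plan says.** Section 2.2, Aim 1, measures energy intake in two ways. The first combines doubly labeled water with "change in maternal energy stores by whole-body MRI and fetus size by 3-D ultrasound". The second is "our energy balance model of gestational weight gain and energy intake", which is not stated to need MRI.

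For the first method, 8.12 takes fat mass from MRI and obtains total fat-free mass by subtracting it from body mass. Section 8.13 then adds total daily energy expenditure (TDEE) to the late-minus-early change in both compartments, weighted by 9300 and 771 kcal/kg. Section 8.14 uses late-visit fat mass and fat-free mass to predict late expenditure; the adjusted outcome is measured minus predicted.

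Section 8.8.3 fixes the scanner geometry: "a field of view of 50 cm will be utilized for the scan". Section 10.1 foresees "the inability to perform MRI in some subjects late pregnancy, due to limitations with the field of view". It states "we require a minimum of 51 subjects", "to detect a between group difference of 590 kcal/d with 90% power or 520 kcal/d with 80% power", and allows for early deliveries, failed scans and Low Gainers together: "10% of subjects will gain less weight than recommended; we aim to complete at least 60 subjects". Section 3 adds "we will enroll up to 75 obese, pregnant women to complete at least 60".

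Section 10.2 names mixed models, analysis of covariance and a Bland-Altman comparison of the two intake methods. It gives no analysis set, imputation, substitute measure or sensitivity analysis for a missing late scan. The only general remark on missing data is in 9.3, under stopping rules, and concerns effects on power.

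**The concern.** A woman without a late MRI has no late fat mass, hence no energy-balance intake and no adjusted expenditure. She also drops out of the Bland-Altman comparison, which needs both intake values. The mixed model does not rescue her: 8.13 produces a single early-to-late value per woman, so there is no partial pregnancy value to borrow from.

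The cause is a fixed field of view in women with a BMI of at least 30, scanned at 35-37 weeks, so the loss is plausibly related to body size. The groups compared are defined by weight gain. If size is also related to intake, the High-minus-Normal difference among scanned women need not equal the difference among all High and Normal Gainers. Completing more women protects power; it does not address that. A rule chosen once it is known who is missing could also be questioned.

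These women are otherwise well measured. Late TDEE, weight and BOD POD, and early and mid-pregnancy MRI, are all on the schedule in section 7.

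**Working it through.** **Inputs from 10.1:** SD 700 kcal/d, two-sided alpha 0.05, High:Normal ratio 1:2, minimum 51, 10% Low Gainers (excluded from the primary analysis by 8.11), at least 60 completers. From section 3: at most 75 enrolled. The MRI failure rate is not given; 10-20% below is an assumption.

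**1. Reproducing Table 4.** Power comes from the noncentral t with SE = 700 × √(1/n₁ + 1/n₂). At 17/34 the SE is 208. Power is 90% for 688 kcal/d and 79% for 590, matching Table 4's .90 and .80 rows. The sentence below the table attaches 90% to 590 and 80% to 520 for 51 women; the calculation gives 79% and 69%. That mismatch is a separate matter, but it is why both 590 and 688 are shown below.

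**2. Margin.** 60 × 0.9 = 54, and 54 − 51 = 3 women (3/54 = 5.6%) to cover failed scans and early deliveries together. If all 75 completed, 75 × 0.9 = 67.5, so 67 would remain, 16 above the minimum. Completers needed to keep 51 evaluable, before any early deliveries: 51/(0.9 × 0.9) = 63 at 10% loss and 51/(0.9 × 0.8) = 71 at 20%.

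**3. Power after MRI loss, starting from 54.**

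| Assumed MRI loss | Evaluable High/Normal | 590 kcal/d | 688 kcal/d |
|---|---|---|---|
| none | 18/36 | 82% | 92% |
| 10% (54 × 0.9 = 48.6) | 16/32 | 77% | 88% |
| 20% (54 × 0.8 = 43.2) | 14/29 | 72% | 84% |

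**4. How much a predicted fat mass matters.** Because total fat-free mass is mass minus fat mass, 1 kg of error in late fat mass moves intake by (9300 − 771)/days = 8529/days. The visits are 19 to 24 weeks apart (week 16 to 35, or week 13 to 37). That gives 8529/168 = 51 to 8529/133 = 64 kcal/d per kg, against an SD of 700. For scale, assume a systematic 3 kg error confined to one group's unscanned women, 10-20% of that group. The group difference would shift by 0.1 × 3 × 51 ≈ 15 to 0.2 × 3 × 64 ≈ 38 kcal/d, against an SE of 202 at 18/36.

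**5. Unit in 8.13 (separate).** The text gives the fat-free-mass change in kg and the coefficient as 771 kcal/kg, but the printed formula takes g/d. For an assumed 6 kg gain over 150 days, kg/d gives 771 × 6/150 = 31 kcal/d; g/d gives 771 × 6000/150 = 30,840 kcal/d.

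**The case against.** The plan foresees failed scans and raises its target from 51 to at least 60, which can fairly be read as an implicit choice of complete-case analysis. That stands as an answer on numbers, not on who is missing.

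The damage is also bounded. A reader might infer that these women's TDEE is thrown away. It is not: absolute expenditure is a primary outcome in its own right (3.1, 8.14), and TDEE feeds both physical-activity measures in 8.15. A reader might also infer that the whole intake comparison rests on women who could be scanned. But mathematical-model intake is analysed in parallel (10.2) and is not stated to need MRI. It is not named as a fallback, yet it is a planned comparison in which these women can count.

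Power looks less fragile at larger differences. It stays at 84% or more for 688 kcal/d. For the preliminary third-trimester difference in 2.1, 3503 − 2617 = 886 kcal/d in overweight women, it is 97% even at 14/29. The three-woman margin applies only if exactly 60 complete, and 60 is a floor.

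Imputation has weaknesses too. Section 8.8.1 stops at body density, with no equation for fat mass, and gives BOD POD error only against hydrostatic weighing. Unscanned women would probably be larger than those who inform the imputation model. These objections argue for using imputation as a sensitivity analysis. They do not remove the need for a stated rule.

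**Conclusion.** The gap is real and of moderate importance. Two MRI-dependent primary outcomes and the method comparison lose women for a foreseen reason that is plausibly tied to body size, and the analysis plan is silent on them.

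It would be tempting to conclude that the High-minus-Normal difference will be biased by a known amount or in a known direction. The documents do not support that: they give no failure rate and no relation between size and intake, and if the two are unrelated there is no bias. Nor do they show that the evaluable number will fall below 51; that depends on how many complete and how many scans fail.

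The power figures of 77-72% (590 kcal/d) and 88-84% (688 kcal/d) rest on exactly 60 completers, 10% Low Gainers, a 1:2 split and the assumed 10-20% loss, shared proportionally between the groups and with no further loss to early delivery.

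The unit slip in 8.13 is certain on the face of the text and would be a thousandfold error in that term if applied literally. The surrounding sentences make the intended unit clear.

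**What to change.** In 10.2:

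- State that the MRI-only analysis is primary for energy-balance intake and adjusted expenditure.
- Pre-specify a sensitivity analysis that multiply imputes missing late fat mass from same-visit BOD POD, weight, early MRI and any mid-pregnancy MRI, TDEE, gain group and the covariates of the analysis model (maternal age, and fetal size and parity if used). Combine each imputed value with the woman's own observed TDEE and pool by Rubin's rules.
- State the equation that converts BOD POD density to fat mass.
- Report the number and body size of women without a late MRI by gain group, and show mathematical-model intake in all women beside the MRI-based results.

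The cost is protocol wording and a standard imputation step; no new measurement is needed. The downside is reliance on BOD POD tracking MRI in late pregnancy and on extrapolation to women larger than those scanned. Mid-pregnancy MRI may also be missing in the largest women, and the method does not help women who deliver before the late visit. Keeping the MRI-only result as primary limits what rests on these assumptions.

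Separately, correct the fat-free-mass term in the 8.13 formula to kg/d.

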10.2. Data analysis plan

Analyses will be performed in SAS version 9.3 (SAS Institute, Cary, NC). Statistical significance will be set at $p \leq 0.05$.

Aim 1: Mixed models will be used to analyze differences between 'High Gainers' and 'Normal Gainers' with respect to energy intake during pregnancy estimated with the energy balance method. Adjustments for covariates, such as maternal age, fetal size and parity will be made if appropriate. Least square means will be compared with the mixed models contrasts. Energy intake from the energy balance model will be analyzed analogously in the context of repeated measurements. We expect that energy intake by the two methods will all be significantly higher in 'High Gainers' versus 'Normal Gainers'. In addition, the two methods for measuring energy intake will be cross validated with each other and compared with Bland-Altman analysis. Regression analyses will be used to assess the relationship between energy intake during pregnancy and postpartum weight loss after 1 year. We predict that lower energy intake during pregnancy is associated with better postpartum weight loss results after 1 year.

Aim 2: Analysis of covariance will be used to assess significance of differential changes ('High Gainers' versus 'Normal Gainers') in absolute energy expenditure. Differential changes in energy expenditure after adjustment for changes in maternal and fetal size will be tested analogously. For secondary hypotheses, change in energy expenditure attributable to accelerometer-measured physical activity (steps per min) will be analyzed to investigate its role in differential energy balance in 'High Gainers' versus 'Normal Gainers'.

Analyses of exploratory aims: The change in determinants of energy intake and energy expenditure in blood and urine from early to late pregnancy and 12 months postpartum will be analyzed by repeated measures with IOM classification and time interactions. Adjustments for covariates, such as maternal age, fetal size, parity and early pregnancy values will be made if appropriate. To control for type I error, statistical significance for all multiple comparisons will be adjusted using the Tukey-Kramer method.

11. SUBJECT PAYMENT

MomEE subjects will be compensated \$600 for completing the study; \$200 after completing the early pregnancy assessments, \$200 after delivery, and the remaining \$200 at the completion of the study. In addition, up to \$25 will be compensated to infant participants for completion of the infant delivery visit before the infant reaches 10 days of life. If the parent/legal guardian reports that the infant participant has a social security number at the time of the infant delivery visit, the infant social security number will be obtained for check processing, and the infant participant will be paid. If the parent/legal guardian reports that the infant participant has not yet obtained a social security number at the time of the study visit which is likely for infants of this age, the parent/legal guardian of the infant participant will be allowed to receive payment on behalf of the infant participant only if the parent/legal guardian agrees to provide his/her own social security number as it is required for check processing.

